6.2 Toxicity Management

The toxicity management of AEs, including AESI consists of safety monitoring (review of AEs on an ongoing basis, and periodical/ad hoc review of safety issues, interruption of study drug dosing with

appropriate clinical management if applicable, and discontinuation of the subjects from the study drug). The management of specific AEs and laboratory parameters is described below.

Management of Serious Infections

Subjects should be closely monitored for the development of signs and symptoms of infection during and after treatment with study drug. Study drug should be interrupted if a subject develops a serious infection. A subject who develops a new infection during treatment with study drug should undergo prompt diagnostic testing appropriate for an immunocompromised subject. As appropriate, antimicrobial therapy should be initiated, and the subject should be closely monitored. Study drug may be restarted once the infection has been successfully treated. Subjects who develop active TB must be permanently discontinued from study drug. If a subject develops zoster, or shows infection with or reactivation of any other herpes virus (e.g., HSV, VZV, EBV, CMV), any study drug should at least be temporarily interrupted until the episode resolves, or discontinued as patient safety requires.

Management of Herpes Zoster

If a subject develops herpes zoster, consider temporarily interrupting study drug until the episode resolves. Serious AEs of herpes zoster should be reported as serious infections.

Management of Serious Gastrointestinal Events

Subjects presenting with the onset of signs or symptoms of a gastrointestinal perforation should be evaluated promptly for early diagnosis and treatment. Subjects with acute, spontaneous perforation of the gastrointestinal tract that requires inpatient medical care or urgent surgical intervention (except for appendicitis or mechanical injury) must be permanently discontinued from study drug.

Management of Thrombosis Events

Subjects who develop symptoms of thrombosis should be promptly evaluated and treated appropriately. If the diagnosis of deep vein thrombosis, pulmonary embolus or non-cardiac, non-neurologic arterial thrombosis is confirmed, the subject must be discontinued from study drug.

Management of Malignancy

Subjects who develop malignancy other than NMSC or carcinoma in-situ of the cervix must be discontinued from the study drug. Information including histopathological results should be queried for the confirmation of the diagnosis. Periodic skin examination is recommended for subjects who are at increased risk of skin cancer.

Management of ECG Abnormality

Subjects must be discontinued from study drug for an ECG change considered clinically significant and with reasonable possibility of relationship to study drug, OR a confirmed absolute Fridericia's correction formula (QTcF) value > 500 msec, OR a change of QTc interval > 60 msec from Baseline.

COVID-19

Interrupt study drug in subjects with a confirmed diagnosis of COVID-19. Consider interrupting study drug in subjects with signs and/or symptoms and suspicion of COVID-19. The COVID-19 eCRF must be completed.

Management of Select Laboratory Abnormalities

For any given laboratory abnormality, the investigator should assess the subject, apply the standard of care for medical evaluation and treatment following any local guidelines. Specific toxicity management guidelines for abnormal laboratory values are described in Table 5, and may require a supplemental eCRF to be completed (see Protocol Section 6.1 [Complaints and AEs]). All abnormal laboratory tests that are considered clinically significant by the investigator will be followed to a satisfactory resolution. If a repeat test is required per Table 5, the repeat testing must occur as soon as possible.

 Table 5.
 Specific Toxicity Management Guidelines for Abnormal Laboratory Values

Laboratory Parameter	Toxicity Management Guideline
Hemoglobin	If hemoglobin < 8 g/dL interrupt study drug dosing and confirm by repeat testing with a new sample
	• If hemoglobin decreases ≥ 3.0 g/dL from Baseline, without an alternative etiology, interrupt study drug dosing and confirm by repeat testing with new sample.
	• If hemoglobin decreases ≥ 3.0 g/dL from Baseline and an alternative etiology is known or the hemoglobin value remains in the normal reference range, the subject may remain on study drug at the investigator's discretion.
	If confirmed, continue to withhold study drug until hemoglobin value returns to normal reference range or its Baseline value.
Absolute neutrophil count (ANC)	 If confirmed < 1000/μL by repeat testing with new sample, interrupt study drug dosing until ANC value returns to normal reference range or its Baseline value.
	• Interrupt study drug if confirmed < $500/\mu$ L by repeat testing with new sample. If value returns to normal reference range or its Baseline value, restarting study drug is allowed if there is an alternative etiology identified; documentation should include reason that rechallenge is expected to be safe for the subject.
	Study drug should be discontinued if no alternative etiology can be found.
Absolute lymphocyte counts (ALC)	• If confirmed < 500/µL by repeat testing with new sample, interrupt study drug dosing until ALC returns to normal reference range or its Baseline value.
Total white blood cell count	• If confirmed < 2000/μL by repeat testing with new sample, interrupt study drug dosing until white blood cell count returns to normal reference range or its Baseline value.
Platelet count	 If confirmed < 50,000/μL by repeat testing with new sample, interrupt study drug dosing until platelet count returns to normal reference range or its Baseline value.
AST or ALT	 Interrupt study drug if confirmed ALT or AST > 3 × ULN by repeat testing with new sample and either a total bilirubin > 2 × ULN or an international normalized ratio (INR) > 1.5.
	A separate blood sample for INR testing will be needed to measure INR at the time of repeat testing for ALT or AST. A repeat test of INR is not needed for determination if above toxicity management criteria are met.
	• Interrupt study drug if confirmed ALT or AST > 3 × ULN by repeat testing with new sample along with new appearance of fatigue, nausea, vomiting, right upper

Laboratory Parameter	Toxicity Management Guideline							
	quadrant pain or tenderness, fever, rash, and/or eosinophilia (> 5% increase from baseline).							
	• Interrupt study drug if confirmed ALT or AST > 5 × ULN by repeat testing with new sample for more than 2 weeks.							
	• If ALT or AST > 8 × ULN, interrupt study drug immediately, confirm by repeat testing with a new sample, and contact the TA MD.							
	Subjects with HBc Ab+ (irrespective of HBs Ab status) and negative HBV DNA PCR testing at Study M16-046 Screening who develop the following should have HBV DNA PCR testing performed within one week (based on initial elevated value): ALT: 5 - ALT: 5 - ALT: 6 - ALT: 5 - ALT: 6							
	 ALT > 5 × ULN OR ALT or AST > 3 × ULN if an alternate cause is not readily identified. 							
	 As separate blood sample for HBV DNA PCR testing will be needed at the time of repeat testing for ALT or AST. 							
	A separate blood sample for HBV DNA PCR testing will be needed at the time of repeat testing for ALT or AST. As with INR, a separate tube is needed.							
	A positive result for HBV DNA PCR testing will require immediate interruption of study drug (unless not acceptable by local practices) and a hepatologist consultation should occur within 1 week for recommendation regarding subsequent treatment.							
	Subjects who meet any of the above criteria should be evaluated for an alternative etiology of the ALT or AST elevation and managed as medically appropriate. The investigator should contact the AbbVie TA MD to discuss the management of a subject when an alternative etiology has been determined. The alternative etiology should documented appropriately in the eCRF; study drug should be discontinued if no alternative etiology can be found and ALT or AST elevations persist.							
	For any confirmed ALT or AST elevations > 3 ULN, complete the appropriate supplemental hepatic eCRF(s).							
Serum Creatinine	• If serum creatinine is > 1.5 × the Baseline value and > ULN, repeat the test for serum creatinine (with subject in an euvolemic state) to confirm the results. If the results of the repeat testing still meet this criterion, then interrupt study drug and re-start study drug once serum creatinine returns to ≤ 1.5 × Baseline value and ≤ ULN.							
	For the above serum creatinine elevation scenario, complete the appropriate supplemental renal eCRF(s).							
Creatine Phosphokinase	 If confirmed CPK value ≥ 4 × ULN and there are no symptoms suggestive of myositis or rhabdomyolysis, the subjects may continue study drug at the investigator's discretion. 							
	 If CPK ≥ 4 × ULN accompanied by symptoms suggestive of myositis or rhabdomyolysis, interrupt study drug and contact AbbVie TA MD. 							
	For the above CPK elevation scenarios, complete supplemental increased CPK eCRF.							

Ab = antibody; ALC = absolute lymphocyte counts; ALT = alanine aminotransferase; AST = aspartate aminotransferase; CPK = creatine phosphokinase; DNA = deoxyribonucleic acid; eCRF = electronic case report form; HB = hepatitis B; HBc Ab+ = Hepatitis B core antibody positive; HBs Ab = Hepatitis B surface antibody; HBV = hepatitis B virus; INR = international normalized ratio; PCR = polymerase chain reaction; TA MD = Therapeutic Area Medical Director; ULN = upper limit of normal

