Samples will be obtained for the clinical laboratory tests listed in Table 3. Blood and urine samples will be collected following a minimum 8-hour fast. If a subject is not able to fast when necessary, due to unforeseen circumstances, the non-fasting status will be recorded in study source documentation.

A certified laboratory will be utilized to process and provide results for the clinical laboratory tests. Laboratory reference ranges will be obtained prior to the initiation of the study.

Instructions regarding the collection, processing, and shipping of these samples will be provided by the central laboratory.

A urine dipstick macroscopic urinalysis will be completed by the central laboratory at all required visits. A microscopic analysis will be performed in the event the dipstick results show leukocytes, nitrite, protein, ketones, or blood greater than negative or glucose greater than normal.

If a laboratory test value is outside the reference range and the investigator considers the laboratory result to be clinically significant, the investigator will:

- repeat the test to verify the out-of-range value;
- follow the out-of-range value to a satisfactory clinical resolution.

A laboratory test value that requires a subject to be discontinued from the study drug or requires a subject to receive treatment will be recorded as an AE. The Baseline laboratory test results for clinical assessment for a particular test will be defined as the Week 24 values from Study M16-046 prior to the initial dose of study drug in Study M19-850.

State of Emergency or Pandemic-Related Acceptable Protocol Modifications

During a state of emergency or pandemic situation, if travel restrictions or other changes in local regulations prevent the subject from having blood drawn for laboratory testing at the study site, if possible, arrange for subjects to have laboratory work done at a local lab, hospital, or other facility. Local lab results should be obtained along with reference ranges and kept within the subjects' source documentation. Local laboratory results should be reviewed by the investigator as soon as possible.

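### The hemoglobin lines of Protocol Table 5 overlap without a stated precedence, so in two combinations one line requires interruption while another makes continued dosing optional

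*Protocol*

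**What the plan says.** The hemoglobin row of Table 5 (Protocol Section 6.2) has four lines, numbered here in order of appearance.

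- Line 1: "If hemoglobin < 8 g/dL interrupt study drug dosing and confirm by repeat testing with a new sample". It has no exception for a known cause.
- Line 2: "If hemoglobin decreases ≥ 3.0 g/dL from Baseline, without an alternative etiology, interrupt study drug dosing and confirm by repeat testing with new sample". It has no exception for a value that is still in range.
- Line 3: after a fall of the same size, if "an alternative etiology is known or the hemoglobin value remains in the normal reference range, the subject may remain on study drug", with the decision left to the investigator. It sets no lower limit on the hemoglobin value.
- Line 4: "If confirmed, continue to withhold study drug until hemoglobin value returns to normal reference range or its Baseline value".

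Neither the row nor the text introducing the table ranks these lines. That text asks the investigator to assess the subject and to follow standard of care and local guidelines. Section 5.10 fixes the Baseline for clinical laboratory assessment: it is "defined as the Week 24 values from Study M16-046 prior to the initial dose of study drug in Study M19-850". On the normal range the same section says only: "Laboratory reference ranges will be obtained prior to the initiation of the study".

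**The concern.** Lines 2 and 3 share a trigger, and the two conditions of line 3 are alternatives. A subject with no other cause found but a value still in range therefore satisfies both lines. Line 1 has its own trigger, but a subject below 8 g/dL may also have fallen by 3.0 g/dL or more from a known cause, and then satisfies lines 1 and 3 together.

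What is at stake is consistent handling of a safety parameter in a study whose primary endpoints are safety endpoints. Anemia is an adverse event of special interest (Protocol Section 6.1). Section 2.2 lists hemoglobin changes in both directions among the laboratory effects observed. SAP Appendix C counts hemoglobin below 80 g/L, which is the same 8 g/dL, as potentially clinically important. If sites resolve the overlap differently, the drug taken after the same result depends on the site. It also stays unclear whether a subject who was kept on drug represents a protocol deviation.

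**Working it through.** The plan states no figure here, so the check is logical: apply the four lines to every feasible combination of the conditions they use.

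**Inputs.** Four yes/no conditions from Table 5: value below 8 g/dL; fall of at least 3.0 g/dL from Baseline; alternative cause known; value in the normal range. That gives 2 × 2 × 2 × 2 = 16 combinations. Four of them pair a value below 8 g/dL with a value in range and are dropped, on the assumption that the lower limit of normal exceeds 8 g/dL. This leaves 12.

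**Rules.** Line 1 applies if the value is below 8. Line 2 applies if there is such a fall and no known cause. Line 3 applies if there is such a fall and either a known cause or a value in range.

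| Below 8 | Fall ≥ 3.0 | Cause known | In range | Combinations | Lines that apply | Result |
|---|---|---|---|---|---|---|
| no | no | either | either | 4 | none | no instruction needed |
| no | yes | no | no | 1 | 2 | interrupt |
| no | yes | no | yes | 1 | 2 and 3 | **overlap (a)** |
| no | yes | yes | either | 2 | 3 | may remain |
| yes | no | either | no | 2 | 1 | interrupt |
| yes | yes | no | no | 1 | 1 and 2 | interrupt |
| yes | yes | yes | no | 1 | 1 and 3 | **overlap (b)** |

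The total is 4 + 1 + 1 + 2 + 2 + 1 + 1 = 12, of which 2 overlap. Line 3 can also be parsed as (fall and known cause) or in range. The same two combinations then overlap, and no others.

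**Restart line.** In (a) the value is in range by definition, so a site that follows line 2 meets the in-range limb of line 4 at the moment of interruption. One could answer that a value can only return to a range it has left, so that only the Baseline limb counts; the row does not say this either. In (b) the value is below 8 g/dL and the in-range limb is not met.

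**Examples.**
- (a), with an assumed lower limit of 13.0 g/dL: 16.8 to 13.6 is a fall of 3.2, and 13.6 is in range. From that Baseline the overlap covers values from 13.0 to 16.8 − 3.0 = 13.8.
- (b): 12.5 to 7.8 is a fall of 4.7 to a value below 8. A Baseline of 11 or more guarantees the fall for any value below 8, but lower Baselines qualify too: 10.0 to 7.0 is a fall of 3.0.

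**Reach of (a).** Baseline must be at least the lower limit plus 3.0. For assumed limits of 11.5, 12.0, 13.0, 13.5 and 14.0 g/dL, that is 14.5, 15.0, 16.0, 16.5 and 17.0 g/dL.

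**Why no share of subjects is given.** The share with a high enough Baseline is P(Z ≥ (limit + 3.0 − mean)/SD). With an assumed mean of 15.3 and SD of 1.0 in men:
- limit 13.0: (16.0 − 15.3)/1.0 = 0.7, giving 0.24;
- limit 14.0: (17.0 − 15.3)/1.0 = 1.7, giving 0.04.

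The answer moves sixfold with one assumed input. It also measures only who could enter (a), not who does: the subject must still fall far enough, stay in range and have no other cause.

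**Comparison within Table 5.** The creatinine row interrupts above 1.5 × Baseline and above the upper limit, and restarts only when both are back at or below those marks, so its restart condition cannot already hold at interruption. The CPK row divides by presence or absence of symptoms.

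**The case against.** The best defence of (a) is that line 3 is an exception to line 2. It repeats line 2's trigger. Subjects with a known cause are already outside line 2, so the in-range limb adds something only if it takes in-range subjects out of line 2. Read that way, (a) has one instruction, and the restart difficulty disappears because nobody in range would have been interrupted under line 2. This reading is plausible. It remains an inference, since line 2 is worded as an instruction without that exception.

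For (b), line 1 can be read as a separate, absolute trigger that permission under another criterion does not waive. That is also plausible and also unstated. A reader might infer that if line 3 overrides line 2 it must override line 1 as well. This does not follow, because line 3 shares its trigger with line 2 only. The text simply leaves the question open.

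Three stronger readings are tempting, and the documents do not support them:

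- **The lines give opposite instructions.** They do not. Line 3 is permissive, so a site that interrupts complies with every line. The defect is that one line requires what another makes optional.
- **The restart line is empty.** It has content for every interrupted subject below range. The difficulty is confined to (a), and arises there only if line 2 is followed.
- **The exposure denominators or anemia counts are compromised.** SAP Section 6.0 defines duration as last dose minus first dose plus one day, and the patient-years in Section 10.2.4 build on it, so an interruption followed by restart leaves them unchanged. Anemia events are found by a MedDRA query and the low-hemoglobin criterion by the value itself (SAP Appendices B and C), not by which line a site followed. What can differ directly is tablets taken, and so the compliance ratio in SAP Section 6.0.

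**Conclusion.** The point holds as a drafting conflict of limited extent. Two of 12 feasible combinations fall under both a mandatory and an optional line, with no stated precedence, and two sites could act differently on the same result while each cites the same table. The other ten combinations receive at most one consistent instruction. The finding rests on the wording alone. Its one outside assumption is that a value below 8 g/dL is never in the normal range.

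A reader might want a percentage of subjects affected. The documents supply neither a hemoglobin range nor a Baseline distribution, so none can be given. Line 3's own wording does presuppose that a subject can fall by 3.0 g/dL and stay in range. The row should be corrected because it governs dosing for a parameter tied to an event of special interest, and because correction is cheap. It does not undermine the planned safety summaries. No view is taken on which clinical rule is right.

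**What to change.** The sponsor's medical team should reconcile the hemoglobin lines of Table 5 so that each combination of the four conditions leads to one instruction. The row should say explicitly:

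- whether line 3 is an exception to line 2;
- whether line 3 can apply to a value below 8 g/dL;
- how the restart line reads under whichever choice is made, so that the two agree.

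The clinical content of each choice belongs to the sponsor. The cost is a wording change to one table row and a notification to sites, with the ethics review that Protocol Section 8.1 requires for any amendment. No test, visit or analysis is added.

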6.3 Cardiovascular Adjudication Committee

An independent committee of physician experts in cardiovascular adjudication will be utilized to assess potential cardiovascular and thromboembolic AEs in a blinded manner. Briefly, CAC consists of 11 voting members including 5 cardiologists, 3 neurologists and 3 thrombotics/vascular specialists. The events that are adjudicated are defined in the CAC charter. The Sponsor/CRO will provide the list of events based on the pre-specified search criteria and all relevant information as a case package for CAC adjudication on a monthly basis. Each randomly assigned CAC member will conduct independent review and submit an assessment of the adjudication outcome. Events may be re-adjudicated if clinically relevant data changes or updates occur. If a decision is not reached via independent review for events, a panel meeting may be held for the purpose of adjudication. A CRO is responsible for coordinating all adjudication activities. The details of the composition and process for the CAC are provided in the CAC Charter.

6.4 Other Safety Data Collection

Specific manifestations of AD (i.e., itching, excoriations, oozing, crusting, erythema, etc.) should not be reported as individual AEs if they are considered to be a worsening of the underlying disease; instead, worsening of AD should be reported as the AE.

6.5 SUSAR Reporting

AbbVie will be responsible for SUSAR reporting for the IMP in accordance with global and local guidelines and Appendix A of the Investigator Brochure will serve as the Reference Safety Information (RSI). The RSI in effect at the start of a DSUR reporting period serves as the RSI during the reporting period. For follow-up reports, the RSI in place at the time of occurrence of the 'suspected' Serious Adverse Reaction will be used to assess expectedness.

7 STATISTICAL METHODS & DETERMINATION OF SAMPLE SIZE

7.1 Statistical and Analytical Plans

The statistical methods provided in this protocol will be focused on efficacy and safety summaries. Complete and specific details of the statistical analysis will be described in the Statistical Analysis Plan (SAP), which will be signed off within 30 business days after the first subject is dosed. Furthermore, a Week 16 Interim Analysis will be conducted after all ongoing subjects have completed Week 16 and all data pertaining to Week 16 are cleaned. The statistical analyses will be performed using SAS (SAS Institute Inc., Cary, North Carolina, USA).

7.2 Definition for Analysis Populations

The Intent-to-Treat (ITT) Population consists of all subjects who receive at least one dose of study drug in the study and will be used for the efficacy analyses.

The Safety Population is the same as the ITT Population for this study. This population will be used to provide a comprehensive summary of safety.

7.3 Statistical Analyses for Efficacy

All efficacy endpoints will be summarized in the ITT population.

The ITT Population will be summarized by treatment group as randomized at the Baseline of Study M16-046.

Continuous variables will be summarized by the number of observations, mean, standard deviation, median, minimum, maximum, as well as the 95% confidence intervals (CIs) of the mean values. Categorical variables will be summarized by counts and percentages, as well as the 95% CIs of the percentages.

There will be no statistical testing for all of the efficacy and safety endpoints.

Efficacy assessments will be summarized by Observed Cases (OC) approach. No data imputation will be applied. Observed Cases will not include values after a subject prematurely discontinue from study drug.

Sample Size Estimation

Approximately 600 subjects that complete treatment in Study M16-046 will roll over in this open label treatment extension study. The sample size is determined by the completion of Study M16-046 and the consenting for the extension.

